After passing an initial prescreening, potential participants will provide informed consent and be administered emailed, phone or videoconference-based screening assessments by trained research staff to assess the above inclusion and exclusion criteria. Participants who qualify after completing all screening assessments will then be sent or provided the study materials. This consists of study medication and self-monitoring equipment, including, as needed, a pregnancy test [for females of childbearing age not using contraception], oxygen saturation monitor, automated blood pressure monitor, and thermometer. We will finalize screening (ie confirming medical stability via oxygen saturation monitor, and vital sign measurement) prior to instructing participants to begin taking study medication, after which point (after taking first dose) they are considered "randomized", consistent with Intention to Treat principles.

Study Design

This study will randomize approximately n=152 participants. This study has an initial double-blind phase (to test the drug's effectiveness) followed by an open-label phase (to provide all participants with exposure to the drug, and allow a taper off of it for those initially taking active drug).

Assignment will be 1:1; (1) Active treatment: start and maintain fluvoxamine 100mg, three times daily. May reduce dose (or start at reduced dose) for tolerability reasons; (2) Control: placebo, three times daily. This drug vs placebo phase will last approximately 15 days and will be followed by an open-label fluvoxamine phase that will typically last 6-7 days but could last up to 15 days: 100mg two times daily for 3 days, then 50mg two times daily for 3 days, then discontinue.

Randomization will be stratified by age (we anticipate: 18-44, 45-54, 55-64 and ≥ 65 years, respectively, to reflect the age distribution of ascending risk for severe symptoms requiring hospitalization (https://www.cdc.gov/mmwr/volumes/69/wr/mm6912e2.htm#F2_down) and sex. Final determination of stratification will be made by the biostatistician ([name]). Stratified randomization schedules will be generated by statistician [name].

After the randomized phase, all participants will be followed for approximately 30 days to collect clinical data (i.e., on hospitalization and other clinical outcomes). Thus, total study participation is approximately 45 days (15 days randomized, 30 days follow-up).

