All enrolled participants will also be sent a longterm follow up survey which asks about persistent COVID 19 symptoms, and a PROMIS scale which asks about functioning and quality of life.

Management: To protect research staff, there will be no face-to-face contact with participants; all interactions will be fully-remote via Zoom videoconference and/or phone/text/email, as well as REDCap surveys pushed out to patients via their smartphones or other devices.

For consented participants who start protocolized treatment we will inform their relevant medical providers, such as a PCP, towards the goal of an informed and collaborative management strategy.

As this is a “prevention of clinical deterioration” study, it is anticipated that a minority (~10-15%) of participants will become hospitalized during the study, and that this will most likely occur during the randomized phase. Research staff under the physician investigators’ supervision will provide support including engagement with participants’ caregivers and physicians to ensure timely medical contact and emergency care (including calling 911).

If a study participant develops a decrease in oxygen saturation to less than 90% on room air on >2 readings, persistent increase in respiratory rate to >30 breaths per minute, persistent increase in Heart Rate to > 120 beats per minute, alteration in mentation, or severe worsening in shortness of breath, the research staff will direct them to seek emergency medical care at the nearest emergency department. If none of the above conditions are met, but the research staff still feel that the participant is unwell, one of the physician investigators will evaluate the participant via phone/telehealth and direct them for further care if needed. When a participant is directed to seek emergency medical care, they will be instructed to use a mask if available, and to identify themselves to EMS or to the Emergency Department staff as having been diagnosed with COVID-19.

Safety Assessments

We will assess for adverse events (including serious adverse events) daily via participant self-report during the first 15 days, and then again at the end of the study.

Outcome Assessments

As this is a prevention (of clinical deterioration) trial, the primary endpoint will be a “time to” clinical worsening analysis. Following the intention to treat principle, all participants who are confirmed to have taken at least one dose of study medication are included in the analyses.

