General comments: Fluvoxamine is an antidepressant drug that functions as a selective serotonin reuptake inhibitor (e.g., similar to escitalopram (Lexapro), fluoxetine (Prozac), sertraline (Zoloft), etc – among the most commonly prescribed drugs in the US). Its risk profile below is for chronic use in a psychiatrically ill population; the risks for short-term use in a non-psychiatric population are likely lower. The research team will carefully evaluate co-prescribed drugs as well as OTC medications and caffeine use, to mitigate drug-drug interactions. We anticipate approximately 20% of participants will be on current SSRI/SNRI use at recruitment – will include these individuals, so long as the participant can be safely switched over to fluvoxamine briefly.

Likely risks: none.

Less likely (1-10%): Nausea, Vomiting, Weight loss, Yawning, Loss of appetite, Agitation/Nervousness/Anxiety, Insomnia, Somnolence, Tremor, Headache, Dizziness, Palpitations, Tachycardia (high heart rate), Abdominal pain, Dyspepsia (indigestion), Diarrhea, Constipation, Hyperhidrosis (excess sweating), Asthenia (weakness), Malaise, Sexual dysfunction (including delayed ejaculation, erectile dysfunction, decreased libido, etc.), Xerostomia (dry mouth).

Rare (<1%): Arthralgia, Hallucination, Confusional state Extrapyrmidal side effects (e.g. dystonia, parkinsonism, tremor, etc.), Orthostatic hypotension, Cutaneous hypersensitivity reactions (e.g. oedema [buildup of fluid in the tissues], rash, pruritus), Mania (elevated mood together with reduced need for sleep and increased energy), seizures, Abnormal hepatic (liver) function, Photosensitivity (being abnormally sensitive to light), Galactorrhoea (expulsion of breast milk unrelated to pregnancy or breastfeeding).

Potential risk associated with Breach of Confidentiality:

One risk of participating in this study is that confidential information may be accidentally disclosed. We will use our best efforts to keep the information about participants secure. All private information is stored in secured areas and on encrypted and password-protected servers.

Other risks:

There may also be unknown risks. We will adjust the informed consent process if new risks are identified.

Adequacy of Protection Against Risks

Recruitment and Informed Consent

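### Current SSRI/SNRI users are admitted if they can be safely switched to fluvoxamine, but about half would receive placebo for about 15 days, and no condition asks whether that is safe

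*Combined protocol and SAP*

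**What the plan says.** The rule for people already on an antidepressant stands in the General comments under Potential risks associated with study medication, not in the eligibility list. The plan states "We anticipate approximately 20% of participants will be on current SSRI/SNRI use at recruitment" and will include these people "so long as the participant can be safely switched over to fluvoxamine briefly". The sentence just before it covers other medicines: "The research team will carefully evaluate co-prescribed drugs", together with over-the-counter products and caffeine, for the purpose of limiting drug interactions.

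Study Design sets 1:1 allocation of about 152 participants to fluvoxamine 100 mg three times daily or to "Control: placebo, three times daily". On duration it says "This drug vs placebo phase will last approximately 15 days". An open-label fluvoxamine phase for everyone follows. One of its stated purposes is to "allow a taper off of it for those initially taking active drug".

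On allocation, "Randomization will be stratified by age" and sex. Antidepressant use is not among the anticipated factors, and the final choice is left to the biostatistician.

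The exclusion criteria do not mention antidepressants. The listed drug risks are those of fluvoxamine and do not include discontinuation effects or relapse after stopping another drug.

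**The concern.** The admission rule names one treatment, fluvoxamine, while the design gives two. For a user allocated to fluvoxamine, a switch replaces one serotonin reuptake inhibitor with another, and the rule asks the right question. For a user allocated to placebo, the same switch means stopping the prior drug with nothing in its place for about 15 days, and the rule does not ask about that. Because allocation is blinded, staff cannot apply the rule only to those it fits. It has to hold for both assignments when the person is enrolled.

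At stake is the welfare of the users who receive placebo: possible discontinuation effects and possible return of the condition for which the drug was prescribed. The plan provides a step-down after only about 15 days of fluvoxamine, so it treats leaving this drug class as something to manage. It describes nothing comparable for people leaving a drug that they were already taking at entry.

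**Working it through.** **Plan's own figure.** Inputs from the Power analysis: 20% versus 5% progression, 80% power, alpha 0.05 (taken as two-sided). The pooled two-proportion formula is

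n = [1.96·√(2·p̄·(1−p̄)) + 0.842·√(p1(1−p1) + p2(1−p2))]² / (p1−p2)², with p̄ = 0.125.

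This gives 75.1, rounded up to 76 per group, 152 in total, as stated. The other five rows of the table (90, 108, 131, 160, 199) also reproduce. The sample size is right on its own inputs, and the present point does not touch it.

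**How many people are affected.**

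- Users expected: 0.20 × 152 = 30.4.
- Users on placebo under 1:1 allocation: 30.4 / 2 = 15.2. That is 20% of the placebo arm (15.2 / 76) and 10% of all participants (15.2 / 152).
- If the true share were 10% or 30% (an assumed range around the plan's figure), the placebo count would be 0.10 × 76 = 7.6 or 0.30 × 76 = 22.8.
- Chance spread: if antidepressant use is not a stratification factor, the number of 30 users who fall among the 76 placebo places out of 152 is approximately hypergeometric. Its central 95% range is 10 to 20.

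**What each provision asks about a user allocated to placebo.**

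| Provision | What it covers | Time without the prior drug? |
|---|---|---|
| General comments, switch rule | Safety of moving to fluvoxamine | No |
| General comments, co-medication review | Drug interactions | No |
| Recruitment & retention | PI determination of eligibility | Not stated |
| Exclusion criteria | Unstable comorbidities, open-ended list | Not stated |
| Recruitment and Informed Consent | Discussion with the participant and treatment team | Not stated |
| Management | Informing providers of those who start treatment, "towards the goal of an informed and collaborative management strategy" | Not stated; follows the start of treatment |
| Safety Assessments | Daily self-reported adverse events for 15 days | Detects harm, does not screen for it |
| Minimizing risk | Oversight by physicians who know the drug class | Not stated |

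No row sets a condition for the placebo assignment.

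**Cost of the remedy.** Each 10% of users declined is 0.10 × 30.4 = 3.0 people to replace.

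**The case against.** The strongest reply is that the switch rule is not the only check and that the people who apply it know these drugs. A user must also satisfy the principal investigator and pass an open-ended exclusion for unstable comorbidity. The study is discussed with relevant members of the treatment team, adverse events are collected daily, and physicians expert in the class oversee safety. This stands as far as it goes: a careful investigator could well decline someone who should not stop. But these are general provisions, and the one sentence written for this group directs attention to the wrong question for half of it.

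It is also fair to say that placebo participants do receive fluvoxamine, in the open-label phase. The mismatch is therefore confined to the randomized phase. A further limit is that the plan never says in so many words that users stop their own drug; that is the natural reading of a switch.

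A reader might infer more, on three lines.

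- *Adverse events or the symptom score are biased.* The documents give no rate for discontinuation effects, so any size would rest on assumption. The endpoint and analysis sections plan no between-arm test of adverse events. The symptom score follows presenting symptoms, with the worst at baseline as its focus, so it moves only if one of those is affected.
- *Controls who keep an antidepressant with sigma-1 activity dilute the primary contrast.* This conflicts with the switch wording, and its size depends on the inputs chosen. If half of users take such a drug and it has a quarter or half of fluvoxamine's effect, power falls from 80.5% to 78.9% or 77.3%. If all users do, with half or all of the effect, it falls to about 74% or 66%. If the stated 20% placebo rate already includes users, nothing is lost. Nothing in the documents selects among these.
- *The sample size is wrong.* It reproduces exactly.

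**Conclusion.** The point holds as a gap in participant safety. About 30 of 152 participants are expected to be users, and about 15 of them would spend the roughly 15-day randomized phase on placebo under a rule that tests only the safety of fluvoxamine. The count rests on the plan's own 20% and 1:1 allocation. The claim that they would be without treatment rests on reading a switch as stopping the prior drug.

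The documents do not support extending this to trial validity. No effect on the oxygen-based primary endpoint or on the sample size is shown, and no bias in the secondary outcomes can be sized from what they contain. It is a cheap improvement to the admission rule and the risk information.

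**What to change.** Reword the sentence in General comments, and preferably repeat it in the eligibility criteria. Current SSRI/SNRI users are enrolled only if a study physician judges, before assignment, that stopping the prior drug is safe under either assignment, including about 15 days on placebo without replacement. Users who cannot safely stop are not enrolled. The judgement belongs in screening, before study medication is allocated and sent.

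Add discontinuation effects and relapse of the treated condition to the stated risks and to the consent for these users. The consent form was not available for this review, so check whether it already covers them.

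The rule should not offer continuation of the prior drug as an alternative. That would allow it to be combined with fluvoxamine at up to 300 mg a day, an exposure for which the present wording does not provide. A sensitivity analysis without users is optional and protects no one on placebo. With about 61 per group it would have about 71% power at 20% versus 5%.

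The cost is one reworded rule, an addition to the risk text and one physician judgement per user. A few users would be declined, about 3 for each 10% of users who fail the check, with a small loss of the generalizability that the eligibility rationale seeks. The planned number and the primary analysis do not change.
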